**Sample and Setting.** The proposed study will follow a prospective cohort ( $N = 120$ ) of racially and economically diverse VLBW infants for 6 weeks following birth. The infants will be born to mothers who are English or Spanish speaking and who are 18 years of age or older. VLBW infants will be sampled by convenience from the neonatal intensive care unit (NICU) at Shands Children's Hospital, a Level III tertiary care center. The hospital is part of the University of Florida and includes a 52 bed NICU. The hospital catchment area encompasses north central Florida and southern Georgia, a predominantly rural and semi-rural population. Approximately 100-110 VLBW infants are delivered there per year. In the preliminary study, 70% of mothers consented for the study. Inclusion criteria for the infants are as follows: (1) born at 32 weeks or less of gestational age, (2) birth weight equal to or less than 1,250 grams, and (3) infant receiving some enteral feedings by 72 hours of age and parenteral feedings by 24 hours of age. Exclusion criteria for the infants are as follows: (1) congenital or chromosomal abnormalities, (2) complex congenital heart diseases and congenital anatomic gastrointestinal abnormalities, (3) Infants will be withdrawn from the study if any of the following occur: grossly bloody stools, radiologic evidence of NEC, or other intestinal complications such as perforation.

**Sample Size Determination / Power Analysis.** In the preliminary study, 40 premature, VLBW infants had a mean enteral intake at 14 days of 72 mL/kg/d ( $SD=65$ ). To detect a 50% improvement to 108, we would require 104 evaluable subjects in a non-sequential design for Primary 1.1 to achieve 80% power at  $P=0.05$  (two-sided). To accommodate one interim analysis, we employed the minimax method of Shuster et al (2002), with first look after 66 evaluable subjects have been accrued. If  $|Z|>2.28$  we shall stop for significance. If  $|Z|<1.12$ , the study will be reviewed for possible futility. There will be no stopping for futility. Otherwise, the study will accrue 120 evaluable subjects (54 more). No competing two stage design can achieve a lower worst case scenario average sample size than this one's 89 evaluable. Intent-to-treat will be followed as closely as possible. However, to accommodate dropouts including deaths (15%) and infants who develop NEC (7%) we expect to accrue 160 subjects.

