**Research Procedure.** The procedures used in this study will be the same as those successfully used in the preliminary study. Following consent by the mothers, infants will be randomized, and baseline demographic data will be collected from their medical charts. Over the first 6 weeks of life the following additional information will be collected at specified time periods from their medical charts: weekly enteral intake, days to full enteral feedings (120 mL/kg/d), hours of PN, evidence of PNALD (level of direct bilirubin, alkaline phosphatase, aspartate aminotransferase (AST) and alanine aminotransferase (ALT)), growth indices (weekly weight, head circumference and length), medications, hours with a CVL, episodes of presumed or culture proven LOS (occurring > 7 days of life), days to discharge, evidence of stage 2 or greater NEC, evidence of aspiration pneumonia on chest radiograph, episodes of ventilator associated pneumonia and guaic status of stools. Additionally, one stool sample will be collected at 3 and 6 weeks to test for fecal calprotectin levels. 1mL of blood will be collected during a routine blood draw between 7 and 14 days of life to test for serum gastrin and motilin levels. If ventilated, tracheal aspirate samples will be collected on days 1, 3, 5, 7, 14, 21, 28 and 35 from routine tracheal aspirate suctioning. As kangaroo care is a potentially confounding factor, episodes and duration of kangaroo care between mother and infant will be recorded on the Kangaroo Care log sheet located at the infant's bedside by either the mother or the nurse. See Table 1.

**Aim 1.** The primary aim of this study is to determine the risks and benefits of aspirating RGC and the clinical benefits of omitting aspiration of RGC prior to enteral feedings on the nutritional outcomes of premature VLBW infants. Both groups will have a sign placed on their isolettes stating which group they are assigned to and whether the nurse should or should not aspirate RGC. Although already documented on the infant's flow sheet, the sign will also include an area for the nurse to document the OG/NG insertion depth. Those personnel who are not involved with the study infants will be unable to be blinded since information regarding gastric residual volume and color is placed in the chart by the nursing staff and monitored by clinicians making decisions regarding enteral feeding plans. The PI is a neonatal nurse practitioner in the NICU

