**Aim 3.** Aim 3 will determine the effect of routine RGC aspiration on gastrointestinal function as evidenced by gastrointestinal peptide activity. Serum levels of gastrin and motilin will be measured on all infants between 14 and 21 days depending upon the timing of a routine blood draw. Since all GRCs are not discarded, waiting until between 14-21 days will allow adequate time for potentially one or more GRC to be discarded. 1 mL of blood will be taken during a routine blood test. All samples will be sent to the laboratory at Shands Children's Hospital at the University of Florida for testing, and lab values will be extracted and recorded by the project coordinator.

**Statistical Analysis.** Data will be entered into the RedCap system by the research assistant. For the primary hypothesis (P1.1), the total weekly enteral intake will be compared between the two randomized treatment groups via a two-sided Welch-corrected T-test. For sample sizes of this magnitude, the central limit theorem assures us that this is an assumption-free analysis, even if the underlying population variances differ. An interim analysis of P1.1 will also be done as described in the Power Analysis section below. Secondary hypotheses S1.1-S1.7 will be tested in the same manner as the primary hypothesis P1.1. For secondary Hypothesis S2.1 (S3.1), [S3.2], we shall compare the personal fractions of positive stools (gastrin levels) [motilin levels] respectively via two-sided Welch-corrected T-tests. For secondary hypothesis S2.2, we shall use a repeated measures analysis of variance to compare the groups with respect to week 3 and week 6 calprotectin levels. . Actual P-values will be reported, and each hypothesis will be accompanied by a point estimate and 95% confidence interval estimate for effect size. For descriptive purposes, a P-value of under 5% will be declared significant. The study is powered strictly around the primary hypothesis P1.1. Withdrawal rates will be compared between the treatments in a tertiary manner using survival analysis (time to withdrawal), via a logrank test.

**Expected outcomes.** Based on the preliminary study, it is reasonable to expect that infants who do not receive routine aspiration of RGC will have better nutritional outcomes, evidence of less gastrointestinal bleeding and inflammation, and improved gastrointestinal function.

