**Table 2: Timetable for Collection of Data**

Data	Time Period Collected
Demographic data	Upon entry into study and during 6 week study period
24-hour enteral feeding intake in mL/kg	Weekly for 6 weeks
Time to full feedings	Recorded daily until 120mL/kg/d reached
Hours of PN	Daily for 42 days
Evidence of PNALD	Weekly or biweekly liver function tests (level of direct bilirubin, alkaline phosphatase AST and ALT )for first 6 weeks
Hours of central venous line access	Daily for 42 days
Episodes of late onset sepsis	All incidences of culture proven or presumed (treated for 7-10 days but with negative cultures) for weeks 1-6.
Growth indices	Weekly weights, head circumferences and lengths
Days to discharge	Days infant is hospitalized
Episodes of radiologic evidence of NEC	All incidences for 6 weeks
Results of stool guaiac	Every stool for 6 weeks
Fecal calprotectin levels	3 and 6 weeks
Serum levels of gastrin and motilin	14-21 days
Pepsin level of respiratory aspirate	Day 1,3,5,7,14 21, 28 and 35 in ventilated infants
Evidence of aspiration pneumonia	All radiographs for 6 weeks
Respiratory cultures	All respiratory cultures done on ventilated infants for 6 weeks

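### Secondary t-tests on time to full feeds, time to discharge, PN hours and line hours have no rule for infants who die or are withdrawn first

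*Combined protocol and SAP*

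**What the plan says.** The Statistical Analysis section gives the primary hypothesis a two-sided Welch t-test and adds: "Secondary hypotheses S1.1-S1.7 will be tested in the same manner as the primary hypothesis P1.1". The S hypotheses are not printed. The Research Design section and Table 1 each list eight nutritional outcomes. Removing enteral intake, the primary, leaves exactly seven, among them time to full feeds, PN hours, central-line hours and length of stay. The mapping is an inference, but the count fits.

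Table 1 defines time to full feeds as the first day at 120 mL/kg/d or more, PN and line hours as totals over days 1 to 42, and length of stay as days from birth to discharge. None of these definitions covers an infant who dies or leaves first.

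On loss, the Sample and Setting section says: "Infants will be withdrawn from the study if any of the following occur: grossly bloody stools, radiologic evidence of NEC", and adds other intestinal complications. The sample size section allows 15% for dropout including death and 7% for NEC, and plans 160 accruals for 120 evaluable infants without defining evaluable. On the analysis population it says only: "Intent-to-treat will be followed as closely as possible". The one analysis of loss is a tertiary logrank test on time to withdrawal.

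**The concern.** A t-test needs a number from every infant in the comparison. For time to full feeds and time to discharge, an infant who dies first has none. The same holds for an infant withdrawn first if abstraction stops at withdrawal, and the documents leave that open. Planning 160 for 120 evaluable suggests that leavers are excluded, but Table 2 collects NEC for the full six weeks although NEC triggers withdrawal.

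For PN and line hours the difficulty is the reverse. A number exists, but death makes it small, and small is the favourable direction.

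The withdrawal triggers are gut events after randomization in a trial of a gut-related intervention. Loss could therefore depend on arm and on feeding progress. The plan's appeal to the central limit theorem concerns the distribution of a mean. It does not supply values that do not exist, nor remove selection by death or withdrawal. Each of these outcomes is to be reported with a P-value, a point estimate and a 95% confidence interval, so the handling rule affects published estimates.

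**Working it through.** **The plan's own figures.** Difference 36 (72 to 108), SD 65, 80% power, two-sided 0.05: n per arm = 2 × (1.960 + 0.842)² × 65² / 36² = 51.2, rounded up to 52, so 104 in total, as stated. For accrual, 120 / (1 − 0.22) = 154 and 120 / (0.85 × 0.93) = 152. The stated 160 equals 120 / 0.75, slightly generous and not a shortfall.

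**Scale of the gap.** Of 160 infants, 0.15 × 160 = 24 are budgeted as dropout or death and 0.07 × 160 = 11 as NEC, about 35 in all. The window is 42 × 24 = 1008 hours. A death on day 10 caps PN hours at 10 × 24 = 240.

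**Assumed inputs.** The documents give no loss by arm, no separate death rate and no distribution for time to full feeds. I assumed 80 per arm, loss uniform on days 4 to 28, PN ending at full feeds, and time to full feeds T = 4 + Weibull (shape 1.8) with median 21 days. The scale is 17 / (ln 2)^(1/1.8) = 20.84. The median was anchored to the pilot statement that "40 premature, VLBW infants had a mean enteral intake at 14 days of 72 mL/kg/d" (SD 65). A rough normal reading gives 1 − Φ((120 − 72)/65) = 0.230 at full feeds by day 14; the Weibull gives 1 − exp(−(10/20.84)^1.8) = 0.234.

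**Direct calculation for truncated PN hours.** The mean PN time cut off per leaver is the average, over exit day L, of ∫ from L to 42 of exp(−((t − 4)/20.84)^1.8) dt = 8.48 days, or 203.5 hours. The spurious arm difference is the difference in loss times this:
- 17% v 27%: 0.10 × 203.5 = 20 hours
- 20% v 24%: 0.04 × 203.5 = 8 hours
- deaths only, 5% v 10%: 0.05 × 203.5 = 10 hours

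**Simulated rejection rates with no true effect** (nominal 5%; 8,000 or more replicates at median 21 for the unequal-loss scenarios at 17% v 27% and for deaths only):

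| Outcome and handling | Loss by arm | Rejects |
|---|---|---|
| Any of these, equal loss | 22% v 22% | about 5% |
| PN hours, truncated totals kept | 17% v 27% | about 8.5% (20 h); 7% (14 h) at median 18, 9% (26 h) at median 24 |
| PN hours, leavers excluded, loss unrelated to feeding | 17% v 27% | about 4–5% |
| PN hours, leavers excluded, slower feeders leave more (correlation 0.5) | 17% v 27% | 7.5% (18 h) |
| PN hours, only deaths truncate | 5% v 10% | 6% (10 h) |
| PN hours, only deaths truncate | 10% v 20% | 8.6% (20 h) |
| Time to full feeds, loss unrelated to feeding | 17% v 27% | 5–6%, Welch or logrank |
| Time to full feeds, slower feeders leave more (correlation 0.5) | 17% v 27% | Welch about 7–8% (0.9 days); logrank about 5.6% |
| PN hours or time to full feeds | 20% v 24% | about 5–6% |

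The spurious differences favour the arm that loses more infants. The 10% v 20% deaths row is an upper case, in which the whole 15% budget is deaths.

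**The unstated rule can set the direction.** I also took a different model: mean 18 days, SD 8, exits uniform on days 3 to 42, loss 30% v 14%, sicker infants leaving more. The spurious difference between arms is 1.2 days in favour of the arm with more loss if only completers are analysed. It is 1.1 days against that arm if leavers are scored as day 42.

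Line hours and time to discharge were not simulated; for them the argument is structural.

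**The case against.** The best defence is that these are secondary outcomes, significance at 5% is called descriptive, the study is powered only on P1.1, and a logrank test on withdrawal would expose an imbalance. All of that is so, and it limits severity. But that logrank test compares withdrawal itself and adjusts none of the secondary estimates.

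A second objection is that every distortion above needs an assumed imbalance. That also stands: the documents give only pooled allowances. If leavers are excluded and loss is unrelated to feeding, the t-test on PN hours holds its level.

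Two stronger readings are tempting and should not be drawn.

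- *That a logrank test would recover power.* With 22% loss and a hazard ratio of 1.6, Welch has about 72% power and logrank about 77%, but proportional hazards favour logrank by construction, and with no loss at all the figures are already about 81% v 84%. If the benefit is a shift of 4.3 days, the order reverses: about 76% v 71% for a normal distribution (SD 9.5) and 68% v 55% for the Weibull. The documents do not say which form applies.
- *That recording stops at day 42, so slow feeders are lost.* The Research Procedure section says "Over the first 6 weeks of life the following additional information will be collected at specified time periods from their medical charts", but that list includes days to discharge, which Table 1 counts without a 42-day limit. For time to full feeds, Table 2 is specific: "Recorded daily until 120mL/kg/d reached". A day-42 cut-off for this outcome is not stated.

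**Conclusion.** The concern holds as a gap in the analysis rules with a possible direction of bias. The stated t-tests have no value to use for infants who die before full feeds or discharge, and they can credit the arm with more deaths or gut-related withdrawals with fewer PN or line hours. This rests on the inferred content of S1.1–S1.7 and on the absence of any censoring, competing-event or imputation rule.

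The size is modest and conditional: none to speak of with equal loss, small at 20% v 24%, and up to about 8.5% rejection with 20 spurious PN hours at 17% v 27% if truncated totals are kept. No power gain is claimed for a change of test. A reader might infer that false-positive rates are inflated in general, or that the primary result is compromised. The documents support neither: there is no evidence of unequal loss, and nothing here changes the power calculation for P1.1. Severity is low to moderate; the rules should be fixed before outcomes are compared by arm.

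**What to change.** 1. List S1.1–S1.7. State whether chart abstraction continues after withdrawal, and continue it to day 42 where consent allows. The withdrawal criteria need not change.
2. Analyse time to full feeds and time to discharge in all randomized infants by cumulative incidence curves and cause-specific Cox or logrank. Treat death as a competing event, and gut-related withdrawal too where no later data exist.
3. Keep the Welch test on PN and line hours. Add, as a companion, days alive and free of PN (or line) through day 42, with days after death scored as not free.
4. Show deaths and withdrawals by arm beside each of these results.

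The cost is analysis wording and a little more chart abstraction. Hazard ratios would stand beside mean differences and are less direct to read. Free days mix death with PN use and have less power: 60% v 72% for PN hours, under an assumed 10% deaths in both arms and hazard ratio 1.6. That is why they are a companion and not a replacement. The cause-specific analysis still assumes that any remaining censoring is uninformative, so it reduces the problem without removing it.

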**Table 1. Instruments**

Variable	Measurement
Demographic data	Gestational age, birth weight, maternal history, prenatal and perinatal complications and medication, mode of delivery, Apgar scores, resuscitation at birth and neonatal acuity (SNAP II) score, medications and disease processes associated with decreased intestinal motility, episodes and duration of KC
Nutritional factors (1-8) below	
1. Enteral intake	Weekly 24-hour enteral feeding intake in mL/kg for first 6 weeks; Type of feeding received
2. Time to full feeds	First day infant received $\geq 120$ mL/kg/d of enteral feedings
3. Hours of TPN	Number of hours infant received some PN for days 1-42
4. PNALD	Weekly or biweekly liver function tests (level of direct bilirubin, alkaline phosphatase AST and ALT) for first 6 weeks
5. Hours of central venous line access	Number of hours infant has a central venous line for days 1-42
6. Episodes of late onset sepsis	Episodes of culture proven or presumed sepsis (treated with 7-10 days of antibiotics but with negative cultures) during week 1- 6 weeks of life
7. Growth indices	Weekly weight, length, and head circumference
8. Length of hospital stay	Days infant remains in hospital from birth until discharge
Episodes of NEC	Episodes of radiologic evidence of NEC during the first 6 weeks
Gastrointestinal bleeding and inflammation (1-2) below	
1. Presence of blood in stools	Positive or negative guiac of all stools for first 6 weeks
2. Fecal calprotectin levels	Level of fecal calprotectin at 3 and 6 weeks
Gastrointestinal function	Serum levels of gastrin and motilin at 14-21 days
Respiratory aspiration of gastric contents (1-3) below	
1. Pepsin level in tracheal aspirates	Pepsin level in the tracheal aspirates of ventilated infants on day ,7,14, 21, 28 and 35
2. Presence of aspiration pneumonia	Presence of aspiration pneumonia on all radiographs
3. Presence of ventilator associated pneumonia	Presence of positive tracheal aspirate on ventilated infants

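### Growth is recorded weekly on three indices but is assigned an unadjusted Welch t-test, which loses precision, leaves chance birth-size imbalance uncorrected and does not fix which comparison is reported

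*Combined protocol and SAP*

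**What the plan says.** The primary outcome is to be "compared between the two randomized treatment groups via a two-sided Welch-corrected T-test" (Statistical Analysis). The same section continues: "Secondary hypotheses S1.1-S1.7 will be tested in the same manner as the primary hypothesis P1.1". No covariate is named for any of these tests.

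The text of S1.1-S1.7 is not in the document. Research Design and Table 1 list eight nutritional factors. Taking out enteral intake, which is P1.1, leaves seven, one of which is growth. Growth is therefore very probably one of S1.1-S1.7, but this is an inference.

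Table 1 describes the growth measurement as "Weekly weight, length, and head circumference", and Research Procedure agrees. Neither place says whether the analysed quantity is attained size, change, velocity or a z-score, or which week counts. The data come from hospital charts: "Over the first 6 weeks of life the following additional information will be collected at specified time periods from their medical charts".

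The demographic row of Table 1 begins "Gestational age, birth weight, maternal history", so birth weight and gestational age will be available, but no analysis is said to use them. Eligibility is "birth weight equal to or less than 1,250 grams", with no lower limit. Randomization is by permuted blocks, and no stratification is stated.

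On significance the plan says: "For descriptive purposes, a P-value of under 5% will be declared significant". It also promises a point estimate and a 95% confidence interval for each hypothesis.

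**The concern.** Size some weeks after birth depends partly on size at birth, and these infants may differ widely in birth weight. A two-sample test that ignores birth weight leaves that variation in the error term. A chance birth-size difference between the arms then carries through to the later comparison and can be read as better or worse growth.

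The plan also gives a six-occasion, three-index outcome a test that takes one number per infant, without saying which number. By contrast, calprotectin, with two time points, gets a repeated measures analysis in the same section. If each index and week were tested separately, there would be many chances of a nominally significant growth result. Infants discharged before week 6 would be absent from the later tests.

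At stake are the precision and readability of a secondary outcome, not the primary result.

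**Working it through.** **The plan's own figure.** The only sample-size calculation is for P1.1: difference 108 - 72 = 36 mL/kg/d, SD 65, two-sided 5%, power 80%. Per arm, n = 2 x (1.960 + 0.842)^2 x 65^2 / 36^2 = 51.2, rounded up to 52, so 104 in total. The stated 104 is reproduced. No power is stated for growth.

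**Inputs for growth.** From the documents: 120 evaluable infants, about 60 per arm; three indices; six weeks; 5% per test. Assumed, because the documents give none: birth-weight SD 200 g, week-6 weight SD 350 g, true week-6 difference 120 g, correlation r between birth weight and week-6 weight of 0.6 to 0.8.

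**Validity.** Simulated with 60 per arm and no treatment effect, the unadjusted Welch test has type I error 0.049 (r = 0.7) and 0.052 (r = 0.9), with mean difference about zero. There is no systematic bias.

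**Precision.** The ratio of adjusted to unadjusted SE is sqrt(1 - r^2), that is 0.80, 0.71 and 0.60 at r = 0.6, 0.7 and 0.8. This does not depend on the assumed SDs.

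- Unadjusted SE = 350 x sqrt(2/60) = 63.9 g. Power for 120 g is about Phi(120/63.9 - 1.96) = Phi(-0.08) = 47%.
- Adjusted SE = 51.1, 45.6 and 38.3 g. Power is about Phi(0.39) = 65%, Phi(0.67) = 75% and Phi(1.17) = 88%.
- Simulation with 4,000 runs gives 46% unadjusted and 64%, 74% and 87% adjusted.
- In SD units, the difference detectable with 80% power is 2.802 x sqrt(2/60) = 0.51 unadjusted, against 0.41, 0.37 and 0.31 adjusted.

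**Chance imbalance.** The SE of the birth-weight difference is 200 x sqrt(2/60) = 36.5 g, giving a 95% range of 1.96 x 36.5 = about 72 g either way. At r = 0.7, an imbalance of 72 g shifts the expected week-6 difference by 0.7 x (350/200) x 72 = 88 g. The unadjusted test rejects beyond 1.96 x 63.9 = 125 g. Given that imbalance and no effect, the chance of rejecting in the direction of the imbalance is 1 - Phi((125 - 88)/45.6) = 1 - Phi(0.81), about 20% (16% to 26% for r = 0.6 to 0.8). This describes a trial at the edge of the 95% range, not the average trial.

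**Number of tests.** The ceiling is 3 x 6 = 18. If the tests were independent, the chance of at least one P < 0.05 with no effect would be 1 - 0.95^18 = 0.60. Simulated with adjacent-week correlations of 0.5 to 0.95 and between-index correlations of 0.5 to 0.8 (assumed), it is about 0.20 to 0.50.

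**Discharge.** The documents give no share discharged before day 42, so no estimate is possible. As an illustration only: if the largest infants leave first and 10% to 30% of controls are gone, a true 0.30 SD effect appears as 0.20 to 0.13 SD among those remaining. With no true effect, no bias arises in that scenario.

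**The case against.** The plan fixes a test, not an analysed variable. A Welch test can be run on change, velocity or a z-score, so a reader who infers that raw attained size will be compared goes beyond the text. That stands.

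A reader might also infer that the growth result would mainly reflect birth size. The documents do not support this. Allocation is random, so birth size contributes noise and chance imbalance, not bias, and the P-value and confidence interval already allow for it on average. Birth size accounts for r^2 of the variance: 36%, 49% and 64% at r = 0.6, 0.7 and 0.8, which is more than half only when r exceeds about 0.71. That stands too.

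Nor does the plan say that 18 tests will be run. A promised point estimate for each hypothesis sits better with one summary, the 5% level is called descriptive, and power is claimed only for P1.1. This weakens the multiplicity argument but does not remove it: nothing identifies the one summary, and results below 5% will still be called significant.

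Finally, selective loss through discharge is plausible but has no known size. The losses the plan does quantify are dropout including death (15%) and NEC (7%), under Sample Size Determination / Power Analysis.

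None of this answers the efficiency point. Two prognostic baseline variables are collected and left unused.

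**Conclusion.** The concern holds as one of efficiency and incomplete specification. The stated growth test is valid, but it is less precise than it need be and does not protect this single trial from a chance birth-size difference. Adjustment would make the SE 20% to 40% smaller if r is 0.6 to 0.8; the power figures rest further on the assumed SDs and the 120 g difference. They apply to weight. For length and head circumference the gain depends on how strongly birth weight predicts each, which the documents do not show.

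Up to 18 tests is a ceiling that the plan permits, and the 0.20 to 0.50 false-positive range depends on assumed correlations. Loss through discharge is a possibility of unknown size. The conclusion also depends on growth being among S1.1-S1.7. For a secondary outcome this is a change that should be made; it does not threaten the primary analysis.

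**What to change.** For each index, replace the Welch test with one repeated-measures mixed model on all available weekly values, with treatment, week and treatment-by-week, adjusted for birth weight and gestational age. Report the week-6 treatment contrast, with its confidence interval, as the single test for that index.

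Adjust for birth length or birth head circumference only if it was recorded before randomisation. Table 1 lists neither among the baseline data. Since Randomization allows assignment within 72 hours of life, a first recorded value may come after assignment, and adjusting for it could remove part of an early effect.

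State separately how death and withdrawal are handled. Discharge that depends on recorded size fits a missing-at-random model reasonably well; death and withdrawal for intestinal complications need their own rule.

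This leaves three tests in place of up to 18. If they were independent, the chance of at least one false positive would be 1 - 0.95^3 = 0.14, so the descriptive label should stay.

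The cost is SAP wording: the weekly sizes, birth weight and gestational age are already collected. The downside is that a missing-at-random modelling assumption replaces a plain t-test.

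### Calprotectin, gastrin and motilin are compared with no stated transformation, and calprotectin by an ANOVA that usually drops infants missing one sample; if values are right-skewed and the effect is multiplicative, power is lost

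*Combined protocol and SAP*

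**What the plan says.** The Statistical Analysis section treats the three markers in two ways.

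- Gastrin (S3.1) and motilin (S3.2), together with the stool fraction S2.1: "we shall compare the personal fractions of positive stools (gastrin levels) [motilin levels] respectively via two-sided Welch-corrected T-tests".
- Calprotectin (S2.2): "we shall use a repeated measures analysis of variance to compare the groups with respect to week 3 and week 6 calprotectin levels".

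The only distributional argument in the plan is attached to the t-test for P1.1: "the central limit theorem assures us that this is an assumption-free analysis, even if the underlying population variances differ". Each hypothesis is promised an estimate: "each hypothesis will be accompanied by a point estimate and 95% confidence interval estimate for effect size". Whether that effect is a difference or a ratio is not said. On power, the section states "The study is powered strictly around the primary hypothesis P1.1".

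Nowhere do the documents name a transformation, a rank-based check, a rule for values below the assay limit, or a rule for an infant with only one of the two stool samples. They also give no SD, distribution or expected effect for any of the three markers.

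**The concern.** All three markers are non-negative concentrations, for which a long right tail is a realistic possibility. If an intervention multiplies such a value, a comparison of arithmetic means is noisy because a few high values carry much of the variance. The plan's appeal to the central limit theorem does not answer this: it concerns the error rate of a mean comparison, not its power.

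Calprotectin is the only inflammation measure in Aim 2, and gastrin and motilin make up the whole of Aim 3. The sample size was not set for them, so there is no planned margin from which to absorb an avoidable loss. Leaving the scale unstated also leaves it open to choice once the data are visible.

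Missing samples raise a separate issue for S2.2. Under Sample and Setting, infants are withdrawn for grossly bloody stools, radiologic NEC or other intestinal complications. The power section allows 15% for dropouts including deaths and 7% for NEC. Some infants will therefore have a week-3 stool sample and no week-6 sample, and a classical repeated-measures ANOVA would usually discard the week-3 value.

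**Working it through.** **Plan's own figure first.** The power section gives 104 evaluable infants for P1.1 (72 versus 108, SD 65, 80% power, two-sided 0.05).

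n per arm = 2 × 65² × (1.960 + 0.842)² / 36² = 51.2, rounded up to 52, so 104 in total. The figure reproduces (power at 52 per arm is 80.6%). There is no corresponding figure for calprotectin, gastrin or motilin.

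**Inputs from the documents.** Maximum 120 evaluable infants with about 1:1 allocation, hence 60 per arm; one blood sample for the peptides; two stool samples, at weeks 3 and 6; significance at 5%.

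**Inputs assumed.** Log-normal values; every infant in one arm shifted by a ratio of 1.5; log-SD from 0.6 to 1.2; correlation 0.5 between week-3 and week-6 log calprotectin; all evaluable infants sampled. The S2.2 test is taken as the group effect, which with two complete visits is a pooled t-test on each infant's mean.

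**Log scale, in closed form.** Power ≈ Φ(ln 1.5 / SE − 1.96), with ln 1.5 = 0.4055.

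- One sample, log-SD 0.8: SE = 0.8 × √(2/60) = 0.146; 0.4055 / 0.146 = 2.78; power 79%.
- Mean of two samples, log-SD 0.8: SE = 0.146 × √((1 + 0.5)/2) = 0.126; 0.4055 / 0.126 ≈ 3.21; power 89%.

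**Raw scale, by simulation** (4,000 runs for calprotectin, 6,000 for the peptides), with the log analysis run on the same scenarios. Power, raw versus log:

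| Log-SD | Gastrin or motilin (Welch) | Loss | Calprotectin (group effect) | Loss |
|---|---|---|---|---|
| 0.6 | 92% vs 96% | 4 | 97% vs 99% | 2 |
| 0.8 | 66% vs 78% | 12 | 79% vs 88% | 9 |
| 1.0 | 42% vs 59% | 17 | 56% vs 73% | 17 |
| 1.2 | 27% vs 45% | 18 | 37% vs 56% | 19 |

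Repeat runs agree to within about 2 points; one put calprotectin at log-SD 0.6 at 98% vs 99%, a loss of 1.

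**Validity.** With no true effect and log-normal data, the raw-scale tests reject in 3.7% to 5.1% of runs (log-SD 0.3 to 1.2). They are valid, at worst slightly conservative.

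**Weight of the high values.** In an arm of 60, the three largest squared deviations carry about 33% of the sum of squares at log-SD 0.3, 54% at 0.8 and 67% at 1.2.

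**When only some infants respond** (one sample, Welch, 60 per arm), raw versus log power:

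- 15% of one arm raised 4-fold: 88% vs 71% at log-SD 0.3; 68% vs 44% at 0.5; 34% vs 25% at 0.8.
- 20% raised 5-fold: 92% vs 74% at log-SD 0.5; 65% vs 48% at 0.8; 43% vs 35% at 1.0.

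Here the raw scale has more power.

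**Pooled versus Welch.** At 60 per arm, the two differ by at most 0.3 points of power in every two-visit scenario. With normal data and SD ratios from 1 to 3, the pooled type I error is 4.7% to 5.6%. With a 64/56 split and the smaller arm 1.5 to 3 times as variable, it is 5.6% to 6.5%.

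**Missing samples.** No figure is attached to this part, because the documents give no rate of missing stool samples among evaluable infants.

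**The case against.** The strongest reply is that the log scale is not better in general. It wins when every infant shifts by the same ratio, which is what the main scenario assumes. The Aim 3 text notes that not all residuals are discarded and allows for perhaps one or more by the time of sampling, so exposure among aspirated infants may be uneven. If only some respond, the high values are the signal and a log analysis plays them down. This stands, and it is why a raw-scale comparison should be kept alongside.

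It is also fair that the skew is assumed, that the loss is only 1-4 points at the lowest spread in the main scenario, and that the raw scale is a reading of silence, though a t-test on levels would naturally be run on values as measured. The plan claims no power for these hypotheses and declares significance at 5% only descriptively.

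A reader might go further than the documents allow in three ways.

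- That the ANOVA's equal-variance assumption is itself a defect, since the plan defends its t-tests as sound "even if the underlying population variances differ" and then does not specify Welch for S2.2. At about 1:1 allocation, which the permuted blocks maintain, this has no material effect. Sphericity does not arise with two visits.
- That a few high values will dominate as a matter of fact. No assay spread is given, so this is conditional.
- That Aims 2 and 3 as a whole lose power. Aim 2 also contains S2.1, a stool fraction, to which this point does not apply.

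**Conclusion.** The point holds in a limited, conditional form for S2.2, S3.1 and S3.2. The plan states no scale for three concentration endpoints, and for calprotectin it names a method that usually discards infants with one sample missing. Under log-normal values, a uniform 1.5-fold effect, 60 per arm and a within-infant correlation of 0.5, the cost in power is about 1-4 points at log-SD 0.6 and 9-19 points at log-SD 0.8-1.2. Under a subset response the ranking can reverse. The planned tests are valid on either account, and P1.1 and its sample size are untouched. The case for change rests on fixing the scale in advance and on using all the calprotectin samples, as well as on the conditional gain in power.

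**What to change.** Amend the Statistical Analysis section as follows.

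1. S2.2: replace the repeated-measures ANOVA with a mixed model for log calprotectin at weeks 3 and 6 that uses every available sample. It keeps the week-3 value of an infant lost before week 6. It still assumes that loss is explained by the observed data, which should be stated because withdrawal for bloody stools or NEC may be related to inflammation.
2. S3.1 and S3.2: apply the Welch t-test to log gastrin and log motilin.
3. Report ratios of geometric means with 95% CI, which settles the effect scale for these three hypotheses.
4. Set values below the assay limit to half the limit.
5. Keep the raw-scale Welch comparison and a rank test as sensitivity analyses.

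The cost is a few sentences and no new data. The downside is that the effect becomes a ratio of geometric means and gives less weight to a few very high responders; the raw-scale sensitivity analysis covers that case.
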